### **Pharmacokinetic Analysis Set**

The Pharmacokinetic Analysis Set 1 (PAS-1) consists of all patients who have at least one evaluable pre- or 3 hours post-dose PK concentration (deferasirox) regardless of whether the pre-dose was taken under the original or current protocol instructions.

A PK concentration is considered evaluable if it fulfills all of the following criteria:

- The actual dose or leading dose prior to pre-dose or post-dose sampling must be as planned by protocol and be documented. In addition, the patient should have received the same dose during the last 4 days prior to the PK sampling (except for Week 1 Day 1).
- The elapsed time between dose administration and PK concentration is documented.
- The pre-dose sample should be within  $24 \pm 4$  hours from the previous dose. The 3h post-dose sample should be obtained between 2 and 4 hours post-dose administration.

- The PK concentration must NOT be associated with any vomiting within 4 hours of dosing.

For statistical analysis based on PAS-1, only evaluable PK samples from patients in PAS-1 will be considered.

The Pharmacokinetic Analysis Set 2 (PAS-2) consists of all patients enrolled under the original protocol who have an evaluable PK profile. PK parameters will be calculated by the clinical pharmacologist if a minimum of 12 patients with evaluable PK profile are available.

- An evaluable PK profile is assessed as such by the Clinical Pharmacologist.

For statistical analysis based on PAS-2, only evaluable PK samples from patients in PAS-2 will be considered

## **Reporting**

Frequency counts and percentages (using FAS-3 or Safety Set 4 as denominator) of patients in each of the above defined analysis sets will be summarized. In addition, listings of patients excluded from each of the analysis sets will be provided.

### **2.3 Patient demographics and other baseline characteristics**

The FAS-1, FAS-2, FAS-3 and Safety Set 4 will be used for all patient demographic and baseline characteristic summaries, unless otherwise specified. Summaries will be produced by treatment arm and overall. Listings will be produced by treatment arm for the FAS-3 and Safety Set 4.

#### **Enrollment status**

The number of patients screened and randomized will be summarized respectively by region, country, center and treatment arm on the FAS-3 and Safety Set 4. The number of patients randomized will also be summarized by stratification factor (age group: 2 to <10 years versus 10 to <18 years and prior ICT: Yes versus No) and treatment arm on the FAS-3. IRT versus eCRF stratification factors will be tabulated on the FAS-3.

#### **Basic demographic and other baseline characteristics**

##### **Basic demographic data**

Categorical data (sex, age groups, weight group, race, and ethnicity) will be summarized by frequency counts and percentages. Continuous data (age, weight and height) will be summarized by descriptive statistics.

The following variables will be summarized as a continuous and categorical data:

- Age (years) will be categorized as: 2 to <10 years and 10 to < 18
- Weight (kg) will be categorized as: <20, 20 to <35, 35 to <55, 55 to <75 and  $\geq 75$

The number of patients by sex and age categories and the number of patients by race will be tabulated on the Safety Set 3 and Safety Set 4.

### History of disease

The main underlying disease as well as the time since the diagnosis date will be summarized by treatment arm.

Time since the diagnosis (years) = (Screening visit 1 date – date of diagnosis + 1) / 365.25.

### Prior iron chelation therapy

Frequency counts and percentages will be tabulated by treatment arm, for prior Iron Chelation Therapy (ICT) prior to start of study drug (yes or no), prior Deferasirox (yes or no) and type of last ICT received. Time since last dose of prior ICT will be summarized by descriptive statistics.

Time since last dose of prior iron chelation therapy (days) = (Screening visit 1 date – stop date + 1).

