## 2.2 Rationale for the study design

This is an open-label, randomized, multicenter, two arm, phase II study. Female and male children and adolescents aged  $\geq 2$  and  $< 18$  years at enrollment with any transfusion-dependent anemia requiring chelation therapy due to iron overload, and a treatment goal to reduce iron burden will be enrolled in this study.

Children and adolescents who are chelation naïve (sample size of at least 96 patients) and those previously treated with iron chelators (maximum sample size of 120 patients) can participate in this study. The addition of the previously chelated patients will allow for an assessment of safety and efficacy between the two populations.

A washout period of 5 days prior to randomization is required for previously treated patients.

The randomization will be stratified by age groups and by prior ICT to ensure a balanced distribution of patients to the two treatment arms on stratifying factors: age groups (2 to  $< 10$  years (using ObsRO questionnaires) and 10 to  $< 18$  years (using PRO questionnaires) and prior ICT (Yes/No), as described in [Section 4.1](#).

The core treatment duration of 48 weeks is considered sufficient to assess the compliance, serum ferritin, safety and patient / observer reported outcome (PRO/ObsRO) profiles of the two formulations.

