## 4 Study design

### 4.1 Description of study design

This is a randomized, open-label, multicenter, two arm, phase II study to evaluate treatment compliance and change in serum ferritin over time of a deferasirox granule formulation and a deferasirox DT formulation in children and adolescents aged  $\geq 2$  and  $< 18$  years at enrollment with any transfusion-dependent anemia requiring chelation therapy due to iron overload, and having a treatment goal to reduce iron burden as measured by serum ferritin.

It is a pre-requisite for the patient to provide written consent/assent to participate in this study. Consent will be obtained from patients, parent(s) or legal guardians. Investigators will also obtain patient's consent/assent according to local guidelines. This must be in place prior to performing any study-related procedures or assessments, including those described at the screening visits (Table 7-1).

As described in [Figure 4-1](#), a screening period (from Day -21) will be used to assess eligibility of patients and will consist of two visits at least 7 days apart. All inclusion and exclusion criteria must be evaluated and documented in the source documents as being met and the results of all screening assessments must be available and reviewed by the investigator. Patients whose eligibility is confirmed will be enrolled and any current chelation therapy will be discontinued to undergo a 5-day chelation washout period (only applicable to patients previously treated with iron chelation therapy) prior to commencing a 48-week randomized treatment period with either deferasirox DT (taken as per local label) or deferasirox granule formulation (taken with or without a light meal) beginning on Day 1.

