#### **4.8.4 Incomplete date for last iron chelation therapy**

Stop date:

Imputed date = min (randomization date-1, last day of the month), if day is missing;

Imputed date = min (randomization date-1, 31DEC), if month and day are missing.

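### SAP 2.3 counts time since last prior chelation back from screening visit 1, so protocol-compliant patients still on chelation at screening get negative days

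*SAP*

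**What the plan says.** **SAP Amendment 3, Section 2.3 (prior iron chelation therapy).** The derivation is "Time since last dose of prior iron chelation therapy (days) = (Screening visit 1 date – stop date + 1", and its use is stated as "Time since last dose of prior ICT will be summarized by descriptive statistics". Section 2.3 produces baseline summaries by treatment arm on FAS-1, FAS-2, FAS-3 and Safety Set 4 unless otherwise specified.

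**Protocol 4.1 (sequence).** "a screening period (from Day -21) will be used to assess eligibility of patients", and that period "will consist of two visits at least 7 days apart". Then: "Patients whose eligibility is confirmed will be enrolled and any current chelation therapy will be discontinued to undergo a 5-day chelation washout period". The same section requires all screening results to be available and reviewed.

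**Protocol 2.2 (anchor of the washout).** "A washout period of 5 days prior to randomization is required for previously treated patients". Protocol 6.1.1 counts the washout as part of the screening period, so it comes after the screening visits but before that period ends.

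**SAP 4.8.4 (partial stop dates).** "Imputed date = min (randomization date-1, last day of the month), if day is missing". A parallel rule, with 31 December in place of the month end, applies when day and month are both missing. There is no rule for a wholly missing stop date.

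**Final CSR SAP (February 2024), Section 2.3.2.** Baseline characteristics for Safety Set 4 follow the primary-analysis definitions, so the derivation carries forward to that set. The section also says that the all-patient baseline summaries will not be repeated.

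**The concern.** A variable described as time since last dose should be zero or positive. Here the reference date comes before the event for every patient who was still taking a chelator at visit 1 and followed the protocol. The interval that matters by design runs from the last dose to randomization, and the derivation does not use the randomization date at all.

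What is at stake is the meaning of one descriptive row. Up to 120 of 216 planned patients (120/216 = 56%) are pre-treated. For those still on chelation at screening the row shows negative days, and for those already off it shows positive days. The pooled mean and median then have no clear interpretation. None of the analyses written out in the supplied SAPs sets the chelation stop date against randomization or first dose.

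**Working it through.** The plan states no figure to reproduce, so the check applies the printed formula to every calendar that the protocol allows.

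**Inputs**
- Visit 1 no earlier than Day -21 (Protocol 4.1); Day -23 if the 2-day visit window in Protocol 7.1 is used.
- Visit 2 at least 7 days after visit 1 (Protocol 4.1).
- Stop date no earlier than visit 2, because eligibility needs both visits (Protocol 4.1).
- Washout of 5 days before randomization (Protocol 2.2). No day count is given, so two readings are run: randomization minus stop of at least 5 days, or at least 6 days (five full drug-free days).

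**Algebra.** Let s be the days from visit 1 to Day 1, and t the days from the stop date to Day 1. The SAP value is (-s) - (-t) + 1 = 1 - (s - t). It depends only on the gap from visit 1 to the stop date. The washout interval is t.

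**Sign.** Stopping on visit 1 gives 1. Stopping one day later gives 0, and two or more days later gives a negative value.

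**Range for a compliant patient still on chelation at screening**
- Upper limit: s - t is at least 7, so the value is at most 1 - 7 = -6. Example: visit 1 Day -12, visit 2 and stop on Day -5.
- Lower limit, s = 21, t = 5: 1 - 16 = -15.
- Lower limit, s = 21, t = 6: 1 - 15 = -14.
- Lower limit with the visit window, s = 23, t = 5: 1 - 18 = -17.

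**The value does not identify the washout**
- Visit 1 Day -21, stop Day -6: 1 - 15 = -14, with five full drug-free days.
- Visit 1 Day -16, stop Day -1: 1 - 15 = -14, with none.

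**Patients already off chelation.** A stop 30 days before visit 1 gives 30 + 1 = +31. Averaged with a patient at -15, the mean is (31 - 15)/2 = 8, which describes neither.

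**Imputed dates.** A partial date set to the day before randomization, with visit 1 on Day -21, gives 1 - 20 = -19 under the SAP formula. Under randomization minus stop it gives 1 day, a short washout produced by the imputation rule.

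**After re-anchoring.** Randomization minus stop equals t. For compliant patients on chelation at screening it runs from 5 (or 6) to 21 - 7 = 14 days, and a value below the minimum identifies a short washout directly.

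**The case against.** The best defence is that this is a history item, not a washout check. The derivation directly above it, time since diagnosis, uses the same visit 1 anchor, and neither SAP 2.3 nor 4.8.4 mentions washout. That stands: no text says the row was meant to document the washout. It does not rescue the row, because diagnosis precedes screening and a current chelator's stop date does not.

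A second defence concerns data capture. Protocol 7.1.1.3 collects prior chelation history at Visits 1 and/or 2, and the case report form is not available here. If the form was not updated once chelation stopped, the value would be missing or would rest on a partial date, not on an observed negative interval. This also stands as a limit. The cap in SAP 4.8.4 shows that stop dates after visit 1 are permitted, not that they are common.

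Third, a stop on the day of visit 2 needs same-day results, so -6 is a bound and not a typical value. A longer gap after visit 2 only makes the value more negative.

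A reader might also infer that the 5-day washout cannot be verified. The documents do not support that. If the stop date is recorded, the interval can be derived from it and the randomization date. SAP 2.4 tabulates and lists protocol deviations, and the full deviation list, in VAP Module 3, was not supplied and may include a washout check.

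**Conclusion.** The derivation is wrong as written, with small consequences. For a protocol-compliant patient still on chelation at screening, the value is -6 days or lower, and between -15 and -6 with visit 1 no earlier than Day -21. This assumes that the actual stop date is recorded and that chelation is not stopped before visit 2. Patients already off chelation at visit 1 get positive values, so it would be incorrect to say that everyone who meets the washout goes negative. The documents do not give the number still on chelation at screening; 120 is the planned ceiling for all pre-treated patients.

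The effect stops at one descriptive baseline item. Both co-primary analyses are in chelation-naive patients (FAS-1), and SAP 2.11 foresees no direct efficacy comparison of the formulations in pre-treated patients.

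Two further inferences are tempting and should not be drawn. One is that residual drug contaminates the Week 1 pre-dose sample: the documents give no elimination figure on which to judge this. The other is that the arms may differ systematically in washout: Protocol 6.1.1 has the washout completed before randomization, so under the plan any difference would arise by chance.

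**What to change.** - Define the variable as randomization date (or first dose date) minus stop date, in days. State the day-count convention and reconcile it with the protocol's 5-day washout, which can be read in two ways.
- Summarize it by arm in FAS-2 and FAS-3.
- Base any count of short washouts on complete stop dates only. Report separately how many dates were partial or missing, and reconcile the SAP 4.8.4 cap with the washout requirement.
- Because the primary analysis has been reported, a corrected row or a footnote to the existing table is enough. Apply the same definition wherever the final CSR SAP reuses it for Safety Set 4.

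The cost is one formula and one table row. No new data are needed, provided that the stop date was recorded after chelation ended; the sponsor should confirm this from the case report form.

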### History of blood transfusion

Descriptive statistics will be tabulated by treatment arm, for total number of blood transfusions received.

### Other baseline characteristics

Descriptive statistics, frequency counts and percentages will be tabulated by treatment arm, as appropriate, for history of splenectomy (yes or no), for hepatic B and C status (see [Table 4-4](#)). In addition, clinically significant abnormality in ECG (yes or no), overall interpretation in echocardiogram (normal or clinically significant or insignificant abnormality), overall interpretation in audiometric test (normal or clinically significant or insignificant abnormality), overall interpretation in ocular exam (normal or clinically significant or insignificant abnormality) will be summarized on the Safety set 3 and 4.

The following continuous variables will be summarized categorically on the Safety Set 3 and 4, and on the FAS-3 and Safety Set 4 for serum ferritin:

- Creatinine will be categorized as:  $\leq$ ULN,  $>$ ULN -  $\leq$ 1.5\*ULN,  $>$ 1.5\*ULN
- Recalculated Creatinine Clearance (CrCl) will be categorized as:  $<$ 40, 40 to  $<$ 60, 60 to  $<$ 90 and  $\geq$ 90mL/min
- ALT and AST will be categorized as:  $\leq$ ULN,  $>$ ULN- $\leq$ 3\*ULN,  $>$ 3\*ULN- $\leq$ 5\*ULN and  $>$ 5\*ULN
- Urine protein/creatinine ratio:  $\leq$ 0.2 mg/mg,  $>$ 0.2-  $\leq$ 0.5,  $>$ 0.5- $\leq$ 1 mg/mg,  $>$ 1 mg/mg
- Serum ferritin will be categorized as:  $<$ 1000,  $\geq$ 1000 to 2500,  $>$ 2500 to 5000,  $>$ 5000 ng/mL.

### Medical history

Medical history and ongoing conditions will be summarized and listed by treatment arm on the FAS-3 and Safety Set 4. Separate summaries will be presented for ongoing and historical medical conditions. The summaries will be presented by primary system organ class,

preferred term and treatment arm. Medical history and current medical conditions will be coded using the Medical Dictionary for Regulatory Activities (MedDRA) terminology.

### **Data presented for screen failure patients**

The total number and the reasons for screen failure (based on reasons recorded in ‘Screening log’ page) will be summarized.

The following listings will be provided for screen failure patients:

- Patient demographics (age, sex, race and ethnicity)
- Patient disposition
- Serious Adverse Events (SAE)

### **2.4 Protocol deviations**

Frequency counts and percentages of patients with any protocol deviation (selection criteria not met, patient not withdrawn as per protocol, treatment deviation, prohibited concomitant medication, other Good Clinical Practice (GCP) deviation) will be tabulated by the deviation type category and treatment arm on the FAS-3 for the core phase and on the Safety Set 4 for the entire granule period. Protocol deviations leading to exclusion of patients from the PPS will be tabulated separately by treatment arm on the FAS-1.

The full list of protocol deviations is documented in the Validation And Planning (VAP) Module 3 document.

All protocol deviations will be listed on the FAS-3 and Safety Set 4.

### **2.5 Patient disposition**

Listings will be produced on the FAS-3 and Safety Set 4.

The summaries of patient disposition during the core phase by treatment arm on the FAS-1, FAS-2 and FAS-3 will show:

- Number (%) of randomized patients who were not treated;
- Number (%) of randomized patients who were treated;
- Number (%) of patients who completed the core phase;
- Number (%) of patients who discontinued the core phase;
- Number (%) for each reasons for core phase discontinuation;

The summaries of patient disposition during the entire granule period by treatment arm on the Safety Set 4 will show in addition:

- Number (%) of patients who entered in the optional extension phase;
- Number (%) of patients who were not treated during the optional extension phase;
- Number (%) of patients who were treated during the optional extension phase;
- Number (%) of patients who completed the optional extension phase;
- Number (%) of patients who discontinued the optional extension phase;
- Number (%) for each reasons for optional extension phase discontinuation;

## 2.6 Treatments (study drug exposure, concomitant therapies)

The Safety Set 1, Safety Set 2, Safety Set 3 and Safety Set 4 will separately be used for medication data summaries unless otherwise specified. Listings will be produced by treatment arm on the Safety Set 3 and Safety Set 4.

### Study drug and study treatment

The terms study drug and study treatment are equivalent and will refer both to deferasirox DT or deferasirox granule.

### Date of first/last administration of study drug

The date of first administration of study drug is derived as the first date when a non-zero actual dose of study drug was administered as recorded on Dosage Administration Record (DAR) Electronic Case Report Form (eCRF). The date of first administration of study drug will also be referred as 'start of study treatment'.

The date of last administration of study drug is defined as the last date when a non-zero actual dose of study drug was administered as recorded on DAR eCRF. This date will also be referred as 'last date of study treatment'.

### Study day

The study day **for safety and pharmacokinetics assessments** (e.g. adverse event onset, laboratory abnormality occurrence, vital sign measurement, Electrocardiogram (ECG), PK concentration, etc.) will be calculated using the start date of study treatment as the reference. For assessments occurring

- **on or after the start date of study treatment**, the study day will be calculated as (date of safety assessment) – (start date of study treatment) + 1. Study day 1 will therefore be the first day of study treatment.
- **before the start date of study treatment**, the study day will be calculated as (date of safety assessment) – (start date of study treatment).

For example, if an adverse event starts 3 days before the start of study treatment the study day displayed on the listing will be negative, i.e. -3.

The study day **for efficacy assessments** (e.g. serum ferritin, PRO) will be calculated using the randomization date as the reference. For assessments occurring

- **on or after randomization date**, the study day will be calculated as (date of non-safety assessment) – (date of randomization) + 1. Then study day 1 will be the day of randomization.
- **before randomization date**, the study day will be calculated as (date of non-safety assessment) – (date of randomization).

The study day will be displayed in the data listings.

## Study drug exposure

Definitions of duration of exposure, total patient-years exposure, average daily dose, cumulative total dose as well as percentage of planned dose taken are defined in [Table 2-2](#):

**Table 2-2 Deferasirox: Study drug exposure**

Overall duration of exposure (day):	$[(\text{date of last study treatment}) - (\text{date of first study treatment}) + 1]$
Drug exposure on dose X (days)	$[(\text{date of last study treatment on dose X}) - (\text{date of first study treatment on dose X}) + 1]$
Average dose (planned and actual, in mg/kg/day):	Mean dose over all days between first and last dose, including interruptions: sum of all (X dose * corresponding duration of exposure on dose X) / overall duration of exposure
Cumulative dose (planned and actual, in mg/kg):	Sum over daily doses of all days between first and last dose
Total patient-years (years):	Overall duration of exposure (days) / 365.25
Percentage of planned dose taken:	$100 \times [\text{Cumulative actual dose} / \text{Cumulative planned dose}]$

The actual dose in mg/kg/day will be obtained by dividing the actual total daily dose administered in the DAR eCRF page by the last available weight at the time of dose administration reported in the vital signs eCRF page.

Overall duration of exposure, average planned and actual daily dose, cumulative actual dose, total patient-years and percentage of planned dose taken will be summarized by treatment arm for the core phase and for the entire granule period.

The following variables will also be summarized by treatment arm and for each phase as appropriate as:

- Duration of exposure will be categorized in the core phase as: <4 weeks, 4 to <12 weeks, 12-<20 weeks, 20-<28 weeks, 28-<36 weeks, 36-<44 weeks,  $\geq 44$  weeks; and in the entire granule period as: <6 months, 6-<12 months, 12-<24 months, 24-<36 months, 36-<48 months,  $\geq 48$  months).
- Deferasirox DT average dose will be categorized as: <15, 15 to <25, 25 to <35 and  $\geq 35$  mg/kg/day
- Deferasirox granule average dose will be categorized as: <10.5, 10.5 to <17.5, 17.5 to <24.5 and  $\geq 24.5$  mg/kg/day

In addition, the number of patients who have dose reduction, increase or dose interruption, with corresponding reasons and the average length of dose interruptions will be summarized.

Dose reduction will be considered if the actual dose is not equal to 0 (or not counted as interruption) and [the planned dose level is lower than the previous non-missing planned dose level Or the dose change is equal to 'yes' and the actual total daily dose administered (mg) is lower ( $> 15\%$ ) than the calculated dose amount based on the planned dose (mg)]. Any dose change to correct a dosing error will not be considered a dose reduction (patient goes back to the previous planned/actual dose after a dose change due to dosing error). Number of reductions will be derived programmatically.

Dose increase will be considered if the actual dose is not equal to 0 (or not counted as interruption) and [the planned dose level is higher than the previous non-missing planned dose level Or the dose change is equal to 'yes' and the actual total daily dose administered (mg) is higher (> 15%) than the calculated dose amount based on the planned dose (mg)]. Note that a dose rechallenge i.e when a patient goes back to the previous planned dose after an interruption or a dose reduction is not considered as an increase.

Dose interruption will be considered if an actual dose of zero in a unit of time between two non-zero actual dosing records. Any rest period as part of the schedule is not considered as an interruption. For the purpose of summarizing interruptions and reasons, in case multiple entries for interruption that are entered on consecutive days with different reasons will be counted as separate interruptions. However, if the reason is the same in this mentioned multiple entries on consecutive days, then it will be counted as one interruption.

Furthermore, box plot of average actual daily dose will be plotted by month and treatment (see [Table 4-1](#) for month definition) on the core phase only.

For each patient, listings of each dose of the study drug administered along with dose change reasons will be produced.

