**Table 6-2 Criteria for interruption and re-initiation of Deferasirox treatment**

Dose modifications for deferasirox	
Body weight	
Increase/decrease of weight by >10% compared to Visit 3 (baseline weight) or body weight at last dose adjustment due to change in patient's body weight	Dose of study medication needs to be adapted using Dosing Table (provided in Appendix 14.2 ). Only when weight changes with >10% compared to baseline weight or body weight at last dose adjustment due to change in patient's body weight, dose needs to be adapted. Smaller variations in body weight (<10%) during study, does not require adjustments in dose. In this case, baseline body weight can be used to calculate correct dose.
Investigations (Renal)	
Serum creatinine and/or creatinine clearance	
Single increase in serum creatinine $\geq 33\%$	Maintain dose level and repeat the assessment at next visit as clinically indicated
For pediatric patients: - Single increase $\geq 33\%$ above baseline value (visit 3/week1) and $> \text{ULN}$  For adult patients: - Increases by 33% or more above the baseline (visit 3/week1) measurement, repeat the serum creatinine within 1 week, and if still elevated by 33% or more	Deferasirox dose reduction by 10 mg/kg/day for the DT and by 7 mg/kg/day for the granules is necessary.
	If after a dose reduction, a progressive increase in serum creatinine beyond the ULN is observed, a treatment interruption is mandated. If after dose reduction/interruption, resolution of serum creatinine occurs ( $< 33\%$ ) at the next study visit and within normal limits, dose can be resumed again at 100%. If increase in serum creatinine reoccurs again within 2 months according to guidelines above, therapy needs to be reduced to 50% of the last dose. After 2 months, if the serum creatinine increase does not recur, study medication can be returned to 100% of the last dose.
Creatinine clearance between 40 and less 60 mL/min	Reduce dose with 50%. If after dose reduction, resolution of creatinine clearance occurs ( $> 60 \text{ ml/min}$ ), dose can be resumed again at 100%.
Creatinine clearance $< 40 \text{ mL/min}$ or serum creatinine increases $> 2$ times the age-appropriate ULN	Deferasirox therapy must be discontinued

Dose modifications for deferasirox	
Investigations (Hepatic)	
Isolated direct (conjugated) Bilirubin elevation	
> ULN – 2 x ULN	Maintain dose level

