**Table 2-2 Deferasirox: Study drug exposure**

Overall duration of exposure (day):	$[(\text{date of last exposure}) - (\text{date of first study treatment}) + 1]$
Drug exposure on dose X (days)	$[(\text{date of last exposure on dose X}) - (\text{date of first study treatment on dose X}) + 1]$
Average dose (planned and actual, in mg/kg/day):	Mean dose over all days between first and last dose, excluding interruptions: sum of all (X dose * corresponding duration of exposure on dose X) / overall number of dosing days
Cumulative dose (planned and actual, in mg/kg):	Sum over daily doses of all days between first and last dose
Total patient-years (years):	Overall duration of exposure (days) / 365.25
Percentage of planned dose taken:	$100 \times [\text{Cumulative actual dose} / \text{Cumulative planned dose}]$

For the core phase only where patients do not enter the extension phase, date of the first administration and last exposure of study drug refer to the first and last dates respectively when a non-zero actual dose of study drug was administered during the study core phase as defined in [Table 2-1](#).

For patients who switch from DT to granules in the extension phase, date of last exposure of study drug in core phase refers to the day prior to the date of the first administration of granules in extension phase (including a zero actual dose) as defined in [Table 2-1](#).

For patients who switch from DT to granules, the date of the first administration of study drug (granules) refers to the first date of granules in the extension phase (including a zero actual dose) to account for treatment interruptions due to efficacy and safety reasons. The last exposure of the granules refers to the last date when a non-zero actual dose of granules was administered during the study extension phase as defined in [Table 2-1](#).

For patients receiving granules throughout the study, the date of the first administration and last exposure of study drug refer to the first and last dates respectively when a non-zero actual dose of study drug (granules) was administered during the study.

The actual dose in mg/kg/day will be obtained by dividing the actual total daily dose administered in the DAR eCRF page by the last available weight at the time of dose administration reported in the vital signs eCRF page.

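### Read literally, the average-dose formula in all three Tables 2-2 is too high whenever a patient resumes an earlier dose value

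*SAP*

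**What the plan says.** Three versions of Table 2-2 are involved.

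- **SAP Amendment 3 (primary analysis), section 2.6.** Exposure on dose X is the difference between "date of last study treatment on dose X" and "date of first study treatment on dose X", plus one day. Average dose, planned and actual, is described as "Mean dose over all days between first and last dose, including interruptions" and computed as "sum of all (X dose * corresponding duration of exposure on dose X) / overall duration of exposure". The next row defines cumulative dose as "Sum over daily doses of all days between first and last dose".
- **End of Core Phase SAP and final CSR SAP.** Average dose now excludes interruptions and is "sum of all (X dose * corresponding duration of exposure on dose X) / overall number of dosing days". Exposure on dose X still runs from first to last date at that dose. Table 3-1 of the End of Core SAP gives the reason for the change: the definition that included interruptions had been an error in the protocol and the primary CSR. Current protocol section 10.3 also leaves out zero-dose days.

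A return to an earlier dose is foreseen. Protocol Table 6-2 says, for example after recovery of creatinine clearance, that the "dose can be resumed again at 100" per cent. Section 2.6 of the SAP has a term for this, dose rechallenge: the case "when a patient goes back to the previous planned dose after an interruption or a dose reduction is not considered as an increase".

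**The concern.** A span from first to last date equals the number of days on a dose only if the patient never leaves that dose and comes back. Once a dose is resumed, the span takes in days spent elsewhere. The formula then no longer delivers the mean over days that its own cell describes, and it disagrees with the day-by-day cumulative dose in the same table.

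At stake are the average planned and actual dose by arm, the average-dose categories, and the monthly box plot of average actual dose (Amendment 3, section 2.6). The average actual dose categories also define subgroups for the supportive ferritin and compliance summaries and the ferritin forest plot (sections 2.8.4 and 2.10, Table 2-6). The patients affected are those whose dose was changed or held and then restored, so any difference between formulations in how often that happens would carry into the exposure comparison.

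**Working it through.** The documents give no numerical average dose to reproduce. The check applies the formula as written to assumed dose histories and compares it with the mean over days. The histories only illustrate the arithmetic; their dose values are ones named in the protocol.

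**Formulas**

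- Literal: for each distinct dose value X, span = last date − first date + 1. Average = Σ(X × span) / D.
- Day by day: average = (sum of daily doses) / D.
- D is all days from first to last dose in Amendment 3, and days with a non-zero dose in the End of Core and final SAPs.

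**A. DT 20 on days 1–84, 10 on days 85–140, 20 on days 141–336.** Spans are 336 days at 20 and 56 days at 10, together 392 against 336 real days.
- Literal: (20 × 336 + 10 × 56) / 336 = 7280 / 336 = 21.67.
- Day by day: (20 × 280 + 10 × 56) / 336 = 6160 / 336 = 18.33.
- The literal value is above the highest dose given. There are no zero-dose days, so all three SAPs give the same answer.

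**B. DT 20 with one 28-day hold in 336 days.** The span at 20 is 336 days; the hold adds nothing under dose zero.
- Amendment 3: literal 20 × 336 / 336 = 20.0; day by day 20 × 308 / 336 = 18.33.
- Later SAPs: literal 6720 / 308 = 21.82; day by day 6160 / 308 = 20.0.
- Changing the denominator while keeping the span gives 21.82 to a patient who only ever took 20.

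**C. DT 20 for 28 days, 30 for 84, 20 for 56, 30 for 168.** Spans are 168 days at 20 and 308 days at 30.
- Literal: (20 × 168 + 30 × 308) / 336 = 12600 / 336 = 37.5.
- Day by day: (20 × 84 + 30 × 252) / 336 = 9240 / 336 = 27.5.
- The category moves from 25 to <35 up to ≥35 mg/kg/day.

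**D. Granules 14, 7, 14 over 168 days, with 28 days at 7.**
- Literal: (14 × 168 + 7 × 28) / 168 = 2548 / 168 = 15.17.
- Day by day: 2156 / 168 = 12.83.
- Again above the highest dose given, though the category (10.5 to <17.5) is unchanged.

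**E. Control without return: DT 20, 25, 30 for 56 days each.** Both methods give 4200 / 168 = 25.0.

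For a given denominator the discrepancy can only be upward, because a span is never shorter than the days spent at that dose. It is zero when no dose value recurs after a gap. Percentage of planned dose taken uses the two cumulative doses and is not affected.

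**The case against.** The strongest reply is that dose X was meant as a single dosing record. The cell describes a mean over days, the neighbouring row sums daily doses, and the Dosage Administration Record (DAR) holds start and end dates for each entry. Section 2.4.1 of the final SAP analyses average dose only for patients with complete dates on every record, a restriction that suits a per-record calculation and that a first-to-last span would not fully need. On that reading the formula equals the day-by-day mean. Programming details sit in separate specifications that are not available here.

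This reading is plausible, and the programs may already follow it. But no Table 2-2 says so, and the row was rewritten for the End of Core SAP with the span left in place. The written rule therefore still permits the wrong value.

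A second reply also carries weight. Actual dose in mg/kg is the daily amount divided by the last available weight, and weight is measured at every visit in growing children. Exact repeats of an actual mg/kg value will be rarer than repeats of a planned level. The Table 2-6 subgroups use actual dose, so the consequence there is weaker than examples with exactly repeated doses suggest.

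Four stronger inferences should not be drawn:

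- *Hold days are counted twice.* They are counted once, at full dose. Under Amendment 3 the average is then too high but does not exceed the dose given.
- *Protocol Table 6-2 orders a return to the earlier dose.* Its wording is largely permissive, and several hepatic rules lead to a reduced dose with no return stated.
- *The PK summaries are distorted.* Section 2.9.3.1 of Amendment 3 mentions the dose categories, but the summaries listed in section 2.9.3.3 are by treatment, visit and time point.
- *Published exposure tables are wrong.* Nothing in the documents shows which reading was programmed.

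**Conclusion.** The point holds as a defect in a written rule. Taken literally, all three Tables 2-2 overstate average dose when the same dose value is resumed. In the illustrations the excess is 3.3 mg/kg/day (18%) for a 56-day reduction in 336 days. For a 28-day hold it is 1.7 mg/kg/day with interruptions included and 1.8 with them excluded. A history with two returns can move a patient up a category.

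These sizes rest on assumed histories with exactly repeated dose values, and on dose X meaning a dose level. How many patients resumed a dose is not given, so the effect on arm-level means cannot be estimated. It is clearest for planned dose.

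The reach is modest: exposure summaries and descriptive, supportive subgroups, which the End of Core SAP does not repeat (section 2.8.4). Neither co-primary ANCOVA uses average dose. The wording should be corrected, but the trial's main conclusion does not depend on it.

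**What to change.** In each Table 2-2, do one of the following:

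- define exposure on dose X as the sum of the lengths of the DAR records at dose X; or
- define average dose as cumulative dose (the sum of daily doses) divided by the stated number of days.

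The denominator should be days with a non-zero dose, in line with current protocol section 10.3 and the End of Core and final SAPs. The including-interruptions version in Amendment 3 has already been superseded.

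Then check the exposure programs against this definition. If they worked record by record, nothing more is needed beyond the clarification. Rerun the exposure and dose-category tables only if the programs followed the literal span. The cost is one line of text and a short program check, plus the rerun if it proves necessary; the record dates needed are already collected.
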